### 2.12.2 Secondary outcomes and subgroup comparisons

Secondary outcomes will be analysed using modelling strategies similar to the primary outcome. Outcomes on a continuous scale will be analysed using linear mixed models, and binary outcomes will be analysed using logistic mixed models. For secondary outcomes which use repeated measurements (T0, T1, and T2), we will include a random effect to account for clustering of measurements within patients.

We will conduct pre-specified subgroup and cross-country comparisons of intervention effectiveness per subgroup analysed. A fixed effect interaction between condition and country will capture differences in effect sizes between country.

Missing values will be replaced according to a chained equations multiple imputations method.

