## 2.10 Data collection procedures

The **primary outcome** (percentage of participating patients readmitted to hospital within 90 days of baseline, or until death if within these 90 days) will be collected via routinely-collected data regarding hospitalization in the patient (electronic) medical record. A data retrieval form will be used to collect data from the patient health record.

Patients and family caregivers enrolled in the study will be asked to complete questionnaires for **secondary outcomes** at baseline (T0, immediately following informed consent), and at 30 and 90 days post-baseline. If a patient dies during the trial, caregivers who consented will be contacted 3 months post-bereavement to complete the VOICES-SF questionnaire. Additional data regarding healthcare utilisation of enrolled patients will be collected through medical notes, consulting the patient's ICLEAR-EU form, and consulting with the general practitioner (GP) or other home/community care when possible and appropriate.

Data for the **cost-effectiveness evaluation** includes the CSRI and EuroQol (EQ-5D-5L) at 30 and 90 days, alongside other trial data collection through the participant interview. Unit costs will be identified first by literature search and, where necessary, by calculation by the research team. The economic evaluation will also utilize the hospital data to model intensity of hospital stay for a given patient profile.

For the **process evaluation**, both quantitative and qualitative data addressing the PRISM/RE-AIM domains will be collected throughout the study (see Table 3 for timing). Quantitative data will be collected using structured checklists, questionnaires, monitoring recruitment numbers, and short surveys; these will be conducted at set time points at the trial timeline and intervention timeline level, including pre-and post-training, after ICLEAR-EU meetings, and at the end of a wedge. Data will be collected via ICLEAR-EU team members attending the trainings and ICLEAR-EU meetings, and from the coordinator and/or clinical champion.

Semi-structured interviews for qualitative data collection will be conducted as follows:

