### 2.12.1 Primary outcome

To determine the effectiveness of the ICLEAR-EU intervention, we will compare the primary outcome between control and intervention participants using a logistic mixed model approach. The model will include a random effect for the cluster, and fixed effects for the condition (control or intervention), country, and time. A fixed effect interaction between condition and time will capture whether effects change over time. A fixed-effect interaction term between country and time will be added to allow for varying secular trends between countries. Gender will be added as a covariate in the analysis, as it has been shown to relate to outcomes in COPD.

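### As worded, section 2.12.2 models the T0 score as an outcome without baseline adjustment or a condition-by-visit term, and its imputation rule has no limit at death

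*Protocol*

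**What the plan says.** Protocol section 2.12.2 sets the general rule: "Secondary outcomes will be analysed using modelling strategies similar to the primary outcome". For the questionnaires it adds: "For secondary outcomes which use repeated measurements (T0, T1, and T2), we will include a random effect to account for clustering of measurements within patients". Section 2.10 places these assessments "at baseline (T0, immediately following informed consent), and at 30 and 90 days post-baseline".

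The primary model in section 2.12.1 has a random hospital effect and fixed effects for condition, country and time. It also has two interactions, country by time and condition by time; of the latter it says "A fixed effect interaction between condition and time will capture whether effects change over time". One patient-level covariate is named: "Gender will be added as a covariate in the analysis, as it has been shown to relate to outcomes in COPD". Neither section names a baseline score as covariate, a visit term, or a condition-by-visit term.

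Section 2.4 sets a patient's condition by the hospital's wedge at consent and baseline, so T0 rows in intervention wedges carry the intervention label.

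On missing data, section 2.12.2 says only: "Missing values will be replaced according to a chained equations multiple imputations method". Deaths during follow-up are foreseen elsewhere. The primary outcome stops at death (2.6.2), QALYs draw on mortality data (2.6.4), all-cause mortality is an outcome (Table 2), and bereaved caregivers are contacted (2.10). Section 2.12 announces an SAP, which is not at hand.

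**The concern.** A score taken just after consent should show little or no effect of an intervention that works over the following weeks. If it is one of three outcome rows and the effect is summarised by one condition coefficient, that coefficient averages a null visit with two informative ones. Quality of life, mood, existential wellbeing, illness perception and carer burden all follow this schedule, and better quality of life is the project's stated aim (section 1). The plan also forgoes the precision to be had from a baseline score that it already collects.

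The imputation sentence raises a smaller, separate matter. A score missing because a living patient did not answer can sensibly be imputed. A score after death does not exist, and filling it in would mix survival with quality of life. The sentence does not separate the two.

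**Working it through.** The protocol gives no figure for the secondary outcomes, so there is none to reproduce.

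**1. What time means in the inherited model.** The primary outcome has one value per patient, and the country-by-time term is there for secular trends. Time in 2.12.1 is therefore trial period, not visit. Condition does not vary within a patient, so the inherited condition-by-time term still compares patients' three-visit averages within a period. It does not isolate T1 or T2.

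**2. Dilution with complete or imputed data.** Assumptions: effect 0 at T0 and δ at T1 and T2; a random patient intercept, hence equal correlation r between visits; visit means fitted; all three rows assigned to the period of enrolment. Each visit then has weight 1/3, whatever r is.
- Effect at T1 and T2: (0 + δ + δ)/3 = 0.667δ.
- Effect at T2 only: (0 + 0 + δ)/3 = 0.333δ.

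**3. Dilution with dropout and no imputation.** Section 2.7 allows for 30% dropout. Assume 85% are seen at T1 and 70% at T2, with monotone loss unrelated to the scores. A patient with n visits gives each of them weight 1/(1 + (n − 1)r). At r = 0.5 the weights are 1, 0.667 and 0.5 for n = 1, 2 and 3.
- T0: 0.15×1 + 0.15×0.667 + 0.70×0.5 = 0.60
- T1: 0.15×0.667 + 0.70×0.5 = 0.45
- T2: 0.70×0.5 = 0.35
- Expected coefficient: (0.45 + 0.35)/1.40 = 0.57δ

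For r from 0.3 to 0.7 the range is 0.58δ to 0.56δ.

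**4. Readings without dilution.** With T0 as a covariate, with T0 as an outcome under a common baseline mean, or with a condition-by-visit contrast at T1 and T2, the expected estimate is 1.0δ.

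**5. Precision (illustrative; hospital clustering and period adjustment ignored, unit variance).**
- Three-visit mean: signal 2/3, variance (1 + 2r)/3.
- Mean of T1 and T2, unadjusted: signal 1, variance (1 + r)/2.
- Mean of T1 and T2 adjusted for T0: signal 1, variance (1 + r)/2 − r².

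Efficiency relative to the adjusted analysis is the ratio of squared signal to variance. For example, at r = 0.5 the three-visit mean gives (0.444/0.667)/(1/0.50) = 0.333, and the unadjusted mean gives 0.50/0.75 = 0.67.

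| r | Three-visit mean | T1/T2 contrast, no T0 covariate |
|---|---|---|
| 0.3 | 0.467 | 0.56/0.65 = 0.86 |
| 0.5 | 0.333 | 0.50/0.75 = 0.67 |
| 0.7 | 0.200 | 0.36/0.85 = 0.42 |

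So a condition-by-visit contrast alone removes the dilution but leaves the baseline information unused.

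**6. Scores after death.** The protocol gives no 90-day mortality. Taking 5% to 15% as an assumption: 1224 × 0.05 = 61 and 1224 × 0.15 = 184 patients without a T2 score because of death. These count the scores open to imputation if the sentence were applied to everyone; they are not a forecast.

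**The case against.** The rule asks for strategies similar to the primary model, not identical ones. Calendar period and visit can stand in one model, and keeping T0 in the outcome vector is a standard longitudinal approach. With a condition-by-visit contrast the dilution is zero, and the SAP may specify one. All of this stands, so the loss is conditional. A reader might infer that every questionnaire effect will be diluted, or that modelling T0 as an outcome is wrong in itself; the protocol supports neither. What remains is that the wording places T0 among the outcomes and names nothing that would protect the contrast.

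A reader might also infer that patients who have died will be given scores, so that effects are partly invented. The protocol does not say this. The inference comes from an unqualified sentence, and elsewhere death is treated as an event in its own right. What stands is that no exemption is written. The sentence's silence on the hospital level in the imputation model is ordinary SAP detail and no fault here.

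That T0 precedes all exposure is likely but not stated. The intervention is delivered at service level (2.5.2), and the figure showing the patient flow is not in the text available. If T0 already reflects some of the effect, the dilution is less than one third, but adjusting for T0 would remove that part of the effect.

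**Conclusion.** The point holds in conditional form and concerns secondary outcomes only. As worded, section 2.12.2 puts T0 in the outcome vector of a model like the primary one, with no baseline adjustment and no condition-by-visit term. Read from a single condition term, a constant effect at T1 and T2 shrinks by one third, and an effect at T2 only by two thirds. This rests on no effect at T0, equal correlation between visits, and complete or imputed data. The loss is nil if a visit-specific contrast is used. Adjusting for the T0 score remains a concrete gain even then.

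The imputation rule is a secondary point: it needs a limit at death. Its size cannot be computed from the protocol.

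**What to change.** In section 2.12.2, and in the SAP to match:

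- Model T1 and T2 as the outcomes, with the T0 score as a covariate.
- Include visit and condition-by-visit terms in addition to calendar period, so that the period adjustment a stepped wedge needs is kept.
- Prefer the covariate to constraining the T0 means to be equal. Hospitals' crossover is disclosed ahead of time (2.9), the respiratory team approaches patients (2.8), and full blinding is not possible (2.9.1). T0 means may therefore differ by condition.
- Limit imputation to values missing while the patient is alive, and report deaths beside the scores.

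The cost is a few sentences before analysis, with no new data. The downside is that while-alive results must be read together with mortality.

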### 2.12.3 Health economic evaluation

Prior to conducting primary analysis of cost-effectiveness, we will examine: (i) baseline differences on characteristics associated with outcome and where necessary control for baseline variables in analysis; and (ii) skewness, kurtosis and heteroscedasticity in the cost data and fit an appropriate (most likely, nonlinear) model. We will account for correlated costs and effects using seemingly unrelated regressions, bootstrapping each set of regressions with 1000 replications, and combining these bootstrapped results in estimating cost-effectiveness acceptability curves. Recognising the uncertainty associated specifically with our trial design, we will employ a stratified two-stage nonparametric bootstrap resampling procedure for clustered data. We will model both costs and outcomes using multi-level models to cluster by country. We will express results in incremental cost-effectiveness ratios (cost per QALY), and cost-effectiveness acceptability curves (probability of cost-effectiveness for different willingness-to-pay thresholds).

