## **2 Methods**

### **2.1 Trial design**

We have chosen a stepped wedge cluster-randomized controlled trial design for this study, which is a pragmatic design that allows every participating hospital the opportunity to receive the intervention.

The stepped wedge cluster-randomized controlled trial will proceed in a similar fashion across the six countries (Belgium, the Netherlands, the United Kingdom, Denmark, Hungary, and Portugal). Clustering is at the level of hospital sites. Each country will include three hospitals. A schematic representation of the trial design is shown in Figure 1.

[figure not shown]

Figure 1. Stepped wedge design of the trial

Each hospital will go through four wedges, each wedge with a duration of six months, for a total of 24 months. Each hospital starts in control condition and crosses over to the intervention condition at 6, 12 or 18 months. The timing of cross-over will be randomly assigned at study onset. Before a hospital crosses over from the control condition to the intervention condition, a 30-day transition period will be integrated into the last control wedge, during which clinicians will receive the intervention training and implementation support will be provided.

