## 2.9 Randomization and allocation

Hospitals will be randomized as to when they cross over from the control condition to the intervention, centrally by UGENT. The full list of 3 hospitals for each country will be randomized at study onset. At 4, 10, and 16 months, the next hospital in the list (Hospital 1, Hospital 2, or Hospital 3) to cross over is unblinded.

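### The cost and QALY models cluster by country, not by the randomised hospital, and section 2.12.3 names no calendar-time term

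*Protocol*

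**What the plan says.** On the economic models, section 2.12.3 states: "We will model both costs and outcomes using multi-level models to cluster by country". Just before that it says: "we will employ a stratified two-stage nonparametric bootstrap resampling procedure for clustered data". It names neither the resampling unit nor the strata. Bootstrap results feed the acceptability curves. On baseline adjustment it plans to look first at differences and then "where necessary control for baseline variables in analysis". No time term is mentioned.

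Elsewhere the unit is clear. Section 2.1: "Clustering is at the level of hospital sites" and "Each country will include three hospitals". Section 2.9: "Hospitals will be randomized as to when they cross over from the control condition to the intervention". The primary model in 2.12.1 has a random effect for the cluster, fixed effects for condition, country and time, and a country-by-time interaction.

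On the EQ-5D-5L schedule, the economic paragraph of 2.10 says that the data "includes the CSRI and EuroQol (EQ-5D-5L) at 30 and 90 days". Table 2 schedules the patient EQ-5D-5L at T0, T1 and T2, and the questionnaire paragraph of 2.10 also includes baseline.

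**The concern.** Country is the only clustering level that 2.12.3 names. Followed as written, the cost and QALY regressions omit the correlation between patients of the same hospital, which is the unit that was randomised. Their standard errors would then be too small.

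In a stepped wedge, condition and calendar time are linked by design. Without a time term, a change over the 24 months in admissions, community care use or utility is credited to the intervention. The primary model guards against this; 2.12.3 does not say that the economic models do.

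Two smaller points affect the QALY equation. The economic data list in 2.10 leaves out the baseline utility that Table 2 collects. Adjusting for baseline only after inspecting differences makes the covariate set depend on the data. At stake are the incremental cost, the incremental QALY and the certainty shown around the cost per QALY. The primary analysis is not affected.

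**Working it through.** Section 2.12.3 gives no figure to reproduce. The layout reproduces the planned total: 18 hospitals x 4 wedges x 17 patients = 1224 (2.7).

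**Inputs.** Six countries with three hospitals each, four six-month wedges, and crossover at 6, 12 or 18 months (2.1). One hospital per country crosses at each step (2.9), so there are 6 hospitals per sequence. Patients per hospital-wedge: n = 17 recruited, or 17 x 0.7 = 11.9 after the 30% drop-out (2.7). The ICC of 0.05 in 2.7 is for readmission. None is given for costs or QALYs, so 0.05 is borrowed, with 0.01 and 0.10 as an assumed range. Cells are taken as equal in size, and the outcome is scaled to total variance 1.

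**Step 1: timing.** Control cells number 18, 12 and 6 in wedges 1, 2 and 3. Intervention cells number 6, 12 and 18 in wedges 2, 3 and 4.

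- Mean control wedge: (18x1 + 12x2 + 6x3)/36 = 60/36 = 1.67
- Mean intervention wedge: (6x2 + 12x3 + 18x4)/36 = 120/36 = 3.33
- Gap: 1.67 wedges x 6 months = 10 months

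A linear trend of d per wedge therefore gives a bias of 1.67d when time is left out; 0.1 SD per wedge looks like an effect of 0.167 SD. With wedge effects the bias is 0. A hospital random effect alone does not remove it: by generalised least squares with 12 patients per cell and ICC 0.05, the same trend gives 0.189 SD.

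**Step 2: standard error.** Let r be the condition indicator after subtracting its overall mean (no wedge effects) or its wedge mean (wedge effects), and let S be the sum of r squared over the 72 cells.

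- No wedge effects: S = 72 x 0.25 = 18
- Wedge effects (wedge means 0, 1/3, 2/3, 1): S = 18 x (0 + 2/9 + 2/9 + 0) = 8

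In both cases r sums over a hospital's four wedges to +1, 0 or -1 for early, middle or late crossover. The squares of these sums total 6 x (1 + 0 + 1) = 12. They cancel within each country, so a country effect does not change the estimate.

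- Model variance, ignoring hospital: 1/(nS)
- True variance: (1 - ICC)/(nS) + 12 x ICC/S²
- (true SE / model SE)² = 1 - ICC + 12 x n x ICC/S

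Example with wedge effects, n = 11.9 and ICC 0.05: 0.95 + 12 x 11.9 x 0.05/8 = 1.8425, square root 1.36.

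| ICC (assumed) | No wedge effects, n = 11.9 / 17 | Wedge effects, n = 11.9 / 17 |
|---|---|---|
| 0.01 | 1.03 / 1.05 | 1.08 / 1.12 |
| 0.05 | 1.16 / 1.23 | 1.36 / 1.49 |
| 0.10 | 1.30 / 1.43 | 1.64 / 1.86 |

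At ICC 0.05 a nominal 5% test, with error 2 x [1 - Φ(1.96/ratio)], errs 9-11% of the time without wedge effects and 15-19% with them. Letting the country effect absorb part of the hospital correlation barely matters: with 12 per cell, true over model SE is 0.0791/0.0675 = 1.17 and 0.1388/0.1012 = 1.37.

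**Step 3: what the bootstrap would do.** The ratios above concern model-based standard errors. If the first stage draws hospitals within countries, the bootstrap targets the true standard error. If it draws whole countries, hospitals are carried along intact, but there are only six units and country cannot also be the stratum. If patients are drawn within countries without regard to hospital, the shortfall passes to the acceptability curve. The text does not say which applies.

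**The case against.** The strongest reply is the bootstrap. Section 2.12.3 justifies it by the trial design, and it feeds the acceptability curves. Since 2.1 defines clustering by hospital, drawing hospitals within country strata is a natural reading. This stands as far as it goes: a reader might infer that the curve will certainly look too precise, and the document does not establish that. But the only level named in 2.12.3 is country, so the better reading has to be supplied by the reader. Nor does clustering by country expressly exclude a hospital level; it simply names none.

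On time, cost per QALY is listed among the secondary outcome measures (1.1), and 2.12.2 says that secondary outcomes follow strategies similar to the primary model. A time term may therefore carry over, and an analysis plan not shown here may state it. That makes the omission a risk rather than a certain bias. Still, 2.12.3 is a separate specification that already departs from 2.12.1 on clustering, so it is unclear which governs.

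The ICC is borrowed from readmission and called conservative there. At 0.01 the shortfall is only 3-12%. The larger ratios at each ICC also assume wedge effects, which 2.12.3 does not mention; read literally, the smaller ones apply.

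Two stronger readings fail. A reader might infer that price inflation is confounded with the intervention. But costs are reported frequencies combined with unit costs (2.6.4), and nothing says that unit costs vary by calendar date. What remains is secular change in resource use or utility. A reader might also infer from 2.10 that the QALY curve has no starting value; Table 2 and the questionnaire paragraph of 2.10 show that EQ-5D-5L is collected at T0.

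**Conclusion.** The point holds for the stated clustering level and the unnamed time term. The clustering sentence in 2.12.3 conflicts with 2.1, 2.9 and 2.12.1. If followed as written, model-based standard errors are too small in every scenario examined, by a factor from 1.03 (ICC 0.01, no wedge effects, 11.9 per cell) to 1.86 (ICC 0.10, wedge effects, 17 per cell). These sizes rest on an assumed ICC, equal cells and a constant within-hospital correlation. Whether the acceptability curve is also too narrow depends on the unnamed bootstrap unit.

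The 1.67d bias follows from the layout alone, but applies only if no time term is fitted and a trend exists; the documents give no value for d. The EQ-5D-5L part is an internal mismatch in one sentence, plus a covariate that should be prespecified. All of this concerns a secondary analysis.

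**What to change.** In 2.12.3, replace clustering by country with hospital as the random level and as the first-stage bootstrap unit, stratified by country. Put country and wedge as fixed effects in both the cost and the QALY equation, as in 2.12.1. Make both changes together, since a hospital effect without time leaves the trend bias in place. With three hospitals per stratum, the plan should also say whether a small-sample correction is used in the resampling.

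Prespecify T0 EQ-5D-5L as a covariate in the QALY equation, whatever the observed baseline differences. Add T0 to the EQ-5D-5L times in the economic paragraph of 2.10, to agree with Table 2.

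The cost is wording and a little analysis work; no new data are needed. The downside is wider reported uncertainty around the cost per QALY. With 12 patients per cell and ICC 0.05, the reported standard error becomes 0.116 SD, against 0.101 SD for a country-only model with wedge effects and 0.068 SD for one without. Most of the second gap is the price of adjusting for time, which the primary analysis already pays. The hospital model is also more efficient than the country-only model with wedge effects, whose true standard error is 0.139 SD.

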### 2.12.4 Process evaluation

Quantitative data (e.g. attendance lists, answers to the S-EOLC and EPCS questionnaires, numbers of included patients, the ICLEAR-EU form and input on short surveys (interval scales on ease of use, satisfaction, etc.) will be analysed descriptively and using inferential statistics ((e.g., mixed methods models due to clustering) depending on the type of data and the analysis rationale. Analyses of qualitative data from the process evaluation will be coordinated by RUMC. Open coding of the qualitative data will be done locally in each country in the English language. A common codebook will

be developed by the RUMC and can be appended by the other research partners. Grouping codes into categories and themes will be done in English, in an international (online) research meeting led by RUMC. All other partners will be involved in the interpretation of findings.

